abuse often feel powerless and “defective” and have greater rates of unprotected sex and decreased self efficacy for protective behaviors such as condom use.(45-47). Fortunately, there is an extensive history of the use of Cognitive Behavior Therapy (CBT) techniques to address maladaptive cognitions and this is a focus of our intervention.(58) The CBT techniques utilized in STAR are designed to focus on identifying automatic thoughts, modify dysfunctional thinking, and promote more realistic adaptive patterns of thinking and behavior that will contribute healthy and safe sexual decision making.

The Importance of Efficacious Programs utilizing new Technologies. Advances in technology have enabled a new wave of novel computer delivered health promotion interventions. Efficacious, face-to-face group interventions have been successfully translated into computer delivered interventions and tested.(61-70) For example, a randomized controlled trial of a 2-hour computer-delivered adaptation of a CDC-DEBI evidence-based group HIV prevention intervention for women found that the intervention resulted in a significantly higher percentage of condom protected sex acts (85.% vs. 52.8%, $p = .03$) (61,62). Another project translated the group intervention SiHLE (Sisters Informing Healing Living and Empowering), a four-session CDC-DEBI for adolescent African American females, into a 2-hour computer-delivered individual intervention. This trial found that the computer intervention significantly improved the proportion of condom use acts as well.(69) These studies, as well as a comprehensive 2009 meta-analysis by Noar, Black, and Pierce, suggest that computer-delivered interventions, including in person interventions that have been translated and digitized, have the potential to be at least as effective as human-delivered interventions in influencing HIV behaviors.(64) Importantly, adolescents are receptive to computer-delivered interventions and, as a result, they are increasingly being advocated for and adopted in the fields of health education and prevention.(70,71) Digitized interventions are also cost effective, as less training, preparation and staff time are required than in human-delivered interventions.(63,70) Computerized interventions are consistently delivered, improving fidelity.(71, 72, 73) and computer audio and graphics components can reach individuals with limited literacy skills, improving the intervention’s reach.(70,74)

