STAR’s 14 group sessions (45 minutes each) were conducted weekly, followed by a final, review session one month later. Groups of four to eight students were led by two trained research staff facilitators, including a clinician with at least a master’s degree in psychology and a Bachelor-level research assistant. The highly scripted sessions used an interactive psycho-educational format of didactic instruction, games, role plays, videos and group discussion. Sessions focused on basic skills relevant to communication, abstinence, and condom use, as well as basic information about HIV, sexuality and health relationships. To address affect management skills, adolescents practiced recognizing and labeling feelings, developed skills to quantify those feelings, discussed negative outcomes of affect dysregulation, and practiced distress tolerance skills in role plays of sexually relevant situations. To enhance cognitive monitoring skills, adolescents practiced recognizing cognitive errors pertaining to HIV risk and learned strategies to counter dysfunctional cognitions such as replacement with healthy thoughts. Youth practiced affect management and cognitive monitoring skills while learning sexuality specific skills (e.g., condom use) and while role playing relevant communication scenarios (e.g., negotiation of condoms, sex refusal). Please see the **Appendix** for the full content and activities.

Setting. The study occurred in fourteen therapeutic schools in southern New England. These schools are a unique setting comprising high-risk youth with mental health issues who have not been able to succeed in traditional school environments. Therapeutic and alternative schools have students with high rates of comorbid psychiatric disorders, substance abuse, learning disorders, and a history of sexual abuse. Many of the youth are in other mental health treatments and the sample shares many of the risk characteristics of youth in various mental health treatment settings.

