Eligibility. Adolescent males and females ages 13 to 20 years who are in mental health treatment will be eligible for enrollment in each phase of study according to the following criteria: 1) English speaking, 2) adolescent assent given to participate in the study, 3) consent of a parent/legal guardian and HIPAA research authorization permission and 4) attending an alternative / therapeutic school, mental health day treatment program, partial hospital program, or therapeutic group homes. Exclusion criteria include: 1) self-report of HIV infection (STAR is not designed to address disclosure, stigma, and medical adherence issues), 2) recent or current pregnancy, 3) cognitive limitation that impairs consent capacity by judgment of clinical staff and 4) current participation in another psychosocial intervention that is addressing STI/HIV prevention.

Community Stakeholders will be eligible for enrollment in the focus group phase of the study according to the following criteria: 1) staff members from a mental health setting, parents of an adolescent in mental health treatment, and staff members from relevant community organizations, such as those serving lesbian, gay, bisexual, transgender, and questioning youth (see letters of support from Bradley Hospital, Gateway Health, AIDS Care Ocean State and Youth Pride Rhode Island), 2) English speaking and 3) consent and HIPAA research authorization permission. Exclusion criteria include: 1) not English speaking and 2) inability to provide consent.

Sample and Recruitment. We will recruit adolescents in Phase 2 from mental health related day programs in southern New England, similar to recruitment for Project STAR. [name] has been highly

successful in recruiting adolescents from these programs for STAR (185 youth enrolled) and for another group HIV prevention intervention (RO1 MH066641), which enrolled 225 youth in mental health treatment. Programs will identify youth in the eligible age range and obtain consent to contact permission from parents / guardians. Research staff will contact the parents / guardians to determine initial eligibility and then screen the adolescent for eligibility. Consent from caregivers and assent of adolescent will be obtained as described in the Human Subjects section. Similar to STAR, we anticipate that 70% of eligible youth who are contacted will be enrolled.

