RCT Stage (months 45-56). D*STAR will be evaluated in comparison to the D*HP control condition through a randomized trial with 120 adolescents in mental health treatment. **Subjects** will be eligible as described in Phase 1, and with no overlap with previously recruited youth. **Settings and Recruitment:** Adolescents will be recruited from mental health related day programs (alternative / therapeutic school, mental health day treatment programs, partial hospital programs, or therapeutic group homes). [name] has been highly successful in recruiting adolescents from these programs for STAR (185 youth enrolled) and for another group HIV prevention intervention (R01 MH066641), which enrolled 225 youth. Programs will identify youth in the eligible age range and will obtain permission to contact parents / guardians. Research staff will contact the parents / guardians to determine initial eligibility and then screen the adolescent for eligibility. Consent from caregivers and assent of adolescent will be obtained as described in the Human Subjects section. Similar to STAR, we anticipate that 70% of eligible youth who are contacted will be enrolled. **Retention:** Procedures will

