All eligible and consented/assented adolescents will complete a demographics form (age, gender, race, ethnicity, parent education, and household income). During Phase 1 all measures will be delivered via paper and pencil. In the Phase 1 Open Trial acceptability and relevance of the sessions will be answered in paper and pencil format, but all other measures will be administered via audio computer assisted self-interview (ACASI) to increase adolescent comfort reporting on sexual and substance use attitudes and behaviors. The ACASI will be administered prior to the start of the intervention, immediately after the intervention, and then 1 month later. In the Pilot and RCT stages of Phase 2, all measures will be administered via computer assisted self-interview (CASI) to increase adolescent comfort reporting on sexual and substance use attitudes and behaviors. The CASI will be administered prior to randomization, immediately after completing the final intervention session, and then 1 month later for the Pilot stage or 3 months later at the RCT stage.

Phase 1: Focus group assessment and Individual Interviews (see guides in the Appendix)

Session Evaluation Form (SEF). The SEF is a brief 13-item questionnaire that will be given to intervention participants at the end of each session. This questionnaire consists of 10 items on a 4-point response scale aimed at eliciting information about the participant's experience with the session (i.e., was the session interesting, was it relevant to their life, did they learn from the session). Three open-ended items query participants about what was most and least useful about the session.(82)

Client Satisfaction Questionnaire–8 (CSQ-8). The CSQ-8 will be used at the completion of the intervention to assess the participant's satisfaction with the intervention, including the procedures, quality and quantity of service, outcome, and general satisfaction. These domains are assessed on a 4-point response scale with individually specified anchors. In addition, three open-ended questions are included that solicit comments about what respondents liked most and least about the intervention. The CSQ-8 has demonstrated high internal consistency across a large number of studies with alpha coefficients ranging from .83 to .93.(83)

Phase 1 Open Trial Measures

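### The plan specifies audio for the Phase 1 Open Trial questionnaires but names only CASI for the pilot and RCT, with no reason given, no reading criterion at entry and no reading support described

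*Combined protocol and SAP*

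**What the plan says.** The opening paragraph of Measures sets the mode of data collection by stage. In the Phase 1 Open Trial the session acceptability forms are on paper, but "all other measures will be administered via audio computer assisted self-interview (ACASI"). For the later stages the text reads: "In the Pilot and RCT stages of Phase 2, all measures will be administered via computer assisted self-interview (CASI"). Each acronym is then used again in the sentence on assessment times. Both modes are given the same purpose, adolescents' comfort in reporting sexual and substance-use attitudes and behaviour. Nothing explains why the mode changes.

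The Phase 2 Eligibility paragraph begins its criteria with "1) English speaking, 2) adolescent assent given to participate in the study". The nearest exclusion is "cognitive limitation that impairs consent capacity by judgment of clinical staff", which concerns consent and not reading. The documents give no reading level for the measures and describe no read-aloud option or staff help.

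Under Preliminary Studies, Setting, the plan says: "Therapeutic and alternative schools have students with high rates of comorbid psychiatric disorders, substance abuse, learning disorders, and a history of sexual abuse". The RCT Stage section lists its settings as "alternative / therapeutic school, mental health day treatment programs, partial hospital programs, or therapeutic group homes". Under Significance, on new technologies, the plan notes that "computer audio and graphics components can reach individuals with limited literacy skills". That remark is about interventions, not assessment.

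**The concern.** All three domains in the RCT hypothesis (sexual behaviour, HIV knowledge and self-efficacy) are self-reported on this instrument. The reading load is considerable, and a youth can meet every entry criterion without being able to read the items comfortably. Misread or guessed answers would make the scores noisier and less responsive to the intervention.

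The plan already specifies a remedy for the Open Trial and then does not name it for the stage where efficacy is tested. Measurement error of this kind cannot be removed once the data have been collected.

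**Working it through.** **1. The two stages side by side.**

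| Item | Phase 1 Open Trial | Phase 2 pilot and RCT |
|---|---|---|
| Mode named in Measures | ACASI (session forms on paper) | CASI |
| Stated purpose | Comfort in reporting | Comfort in reporting |
| Reason for the change | – | None |
| Reading criterion | None | None |
| Reading support described | Audio | None |
| Instruments | ARBA, knowledge, self-efficacy, affect dysregulation, condom advantages, CTQ, BSI | The same, plus YRBSS and cross-talk items |

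**2. Reading load.** For the scales whose length is given in Measures: knowledge 20 + self-efficacy 13 + affect dysregulation 6 + condom advantages 13 + CTQ 28 = 80 items. The ARBA, BSI and YRBSS come on top.

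**3. The plan's only power figure.** Data Analysis gives power 0.8 for the Open Trial with n = 26, effect size 0.5 and a one-tailed paired t-test at 0.05. With 25 degrees of freedom and noncentrality 0.5 × √26 = 2.55, the noncentral t gives 0.798, so the figure reproduces. It does not bear on the RCT, for which no power, alpha or effect size is stated.

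**4. What cannot be computed.** The size of the harm needs the share of weak readers, their extra error and the RCT's assumed effect. The documents give none of these. They quote internal consistency of 0.62 to 0.79 for the brief knowledge and attitude scales, but not by mode or reading level.

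**5. Illustration under stated assumptions.**
- From the documents: 120 youth, and about 85% retention at three months, so 0.85 × 120 = 102.
- Assumed: 1:1 allocation (51 per arm), effect d = 0.5 SD (borrowed from the Open Trial), two-sided alpha 0.05, no clustering by intervention group.
- Assumed: a share f of weak readers whose answers carry extra error variance v, in units of the outcome variance. The SD is then √(1 + f·v), and the sample needed for the same power rises by the factor 1 + f·v.
- Power = Φ( (d/SD) × √(n/2) − 1.96 ).

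With no added error: 0.5 × √25.5 − 1.96 = 0.565, so power is 0.714. With all 60 per arm retained: 0.5 × √30 − 1.96 = 0.779, so power is 0.782.

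| f | v | 1 + f·v | Standardised effect | Power, 51 per arm |
|---|---|---|---|---|
| 10% | 0.25 | 1.025 | 0.494 | 0.703 |
| 20% | 0.50 | 1.10 | 0.477 | 0.673 |
| 30% | 1.00 | 1.30 | 0.439 | 0.600 |

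Across this range the loss is about 1 to 11 percentage points of power, equivalent to needing 2.5% to 30% more participants. These figures show how the loss depends on f and v. They do not estimate it for this trial.

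**The case against.** The strongest reply is that the documents never say audio is removed. CASI may be a loose label: the Open Trial section describes as merely computerized the same assessment that Measures calls ACASI. The stated purpose of audio is comfort, not literacy, and the remark on limited literacy concerns interventions. The learning-disorder statement covers schools only and gives no rate, and a learning disorder is not the same as weak reading. The earlier STAR trial, in therapeutic schools and with laptop self-report (audio neither stated nor excluded), found significant differences between conditions in the Sex Risk Index, HIV knowledge and condom self-efficacy. Those are the domains of the RCT hypothesis, so the scales can detect an effect in such youth.

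Much of this stands, and it rules out several stronger inferences that a reader might draw:
- **The RCT questionnaire is text-only.** This is inferred from the label. The plan does not say it.
- **Weak readers do add noise to every outcome.** This is a plausible risk. The documents contain no data that show it.
- **A given share of youth answers at random, which implies a particular effective sample size.** The documents supply no such share, and the STAR results are no support for so severe a model.
- **Results can no longer be compared with Phase 1.** No pooling or cross-phase comparison is planned. The Open Trial is a single-arm pre-post test of four sessions, while the RCT compares concurrent randomized arms.
- **The arms are biased against each other.** Both use the same mode.

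The reply does not explain the change. The two terms are spelled out a few sentences apart and each is repeated, so on a plain reading audio is specified for one stage and not for the other. STAR's success does not show that unaided reading is adequate here, because its mode is not described in enough detail.

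**Conclusion.** The point holds as an inexpensive improvement to measurement, not as a flaw that threatens validity. The plan names audio for the Open Trial and not for the pilot and RCT. It gives no reason, sets no reading criterion and describes no reading support, although at least one RCT setting type is said to have high rates of learning disorders. Weak readers may therefore add measurement error to the self-reported RCT outcomes, with attenuation and lost precision as the expected result.

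The size is unknown. The illustrative fall in power from 0.71 to between 0.70 and 0.60 rests entirely on the assumed effect, allocation, alpha, share of weak readers and error variance, and it ignores clustering. The conclusion itself does not depend on those numbers. It rests on reading CASI in its ordinary sense, without audio. If the sponsor meant audio to continue, correcting the label settles the matter.

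**What to change.** In Measures, change the sentence on the Phase 2 pilot and RCT so that these measures are administered by ACASI, as in the Open Trial, and add audio for the YRBSS and cross-talk items. Use the same mode in both arms and at all assessments. If audio is left out on purpose, state the reason and the reading help that youth will receive.

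The cost is small. The ARBA, the knowledge and attitude scales, the CTQ and the BSI are already planned for audio in the Open Trial, so only the YRBSS and cross-talk items need new recordings. The downside is headphones at each assessment and a slightly longer interview for some youth.

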During any phase of the study, if research staff determines that a participant is an acute medical or psychiatric risk, the PI or licensed designee will meet with the participant individually for further assessment and notify the participants’ parents of any clinical needs. Staff at the mental health program will also be notified, if indicated. Acute risks would include severe medical illness, or the development of any other severe psychiatric symptoms or disclosure of sexual or physical abuse. Any subjects who exhibit acute risks will be evaluated immediately by emergency room clinical staff at Rhode Island Hospital, or if less acute, by an independent clinician that day. Less severe medical needs or distress can be managed by staff or PI over the phone or with an individual interview. The PI and/or staff will meet with participants and/or families to review concerns and to make referrals for continuing care as needed. Of note, members of the proposed research team have substantial prior clinical (medical and psychiatric) and research experience in care of youth in mental health treatment as evidenced through their biographical sketches.

Potential Benefits of the Proposed Research to the Subjects and Others

Importance of Knowledge to be Gained. We hope that our intervention will be successful in addressing the unique HIV prevention needs of youth in mental health treatment and think that the clear examination of these questions outweighs the previously mentioned risks. The effectiveness of a novel, scalable, technology driven, HIV prevention intervention is understudied with this population. Given that adolescents in mental health treatment are at greater risk for HIV and other STIs than their peers, and the paucity of easily available intervention programs for this population, the knowledge to be gained from this research is significant. The risks to participants are minimal in relation to the importance of the knowledge to be gained.

Reimbursement for Time and Effort. In Phase I participants will be reimbursed \$50 for their participation in the focus group. Qualitative interview participants will be reimbursed 50 for each individual interview, so will receive \$100 if they complete the two sessions. Participants will be reimbursed \$50 for baseline and postintervention assessments during the Phase 1 Open Trial, so will receive \$100 if they complete both assessments. Subjects in all stages will be compensated \$15 for local travel to assessments.

In Phase II participants will be reimbursed \$50 for their participation in the focus group. Qualitative interview participants will be reimbursed \$50 for each individual interview, so will receive a maximum of \$100 if they complete both interviews. Participants will be reimbursed \$50 for baseline and postintervention (immediately after last intervention session and one month postintervention) assessments during the Phase 2

pilot, so will receive \$150 if they complete all three assessments. Participants in the randomized control trial will be reimbursed \$50 for baseline and postintervention assessments (immediately following last intervention session and three month postintervention), so will receive \$150 if they complete all three assessments. Subjects in all stages will be compensated \$10 for local travel to assessments.

Data and Safety Monitoring Plan

To address the NIH policy for Data and Safety Monitoring, the PI has developed a system for oversight of the proposed study and its participants. The Data and Safety Monitoring Plan for this application will begin by implementing standard procedures for day-to-day monitoring of the study. Weekly meetings with the research team will be conducted to evaluate the progress of the trial and to review data quality, recruitment, study retention, and examine other factors that may affect outcome. Participant experiences with the study procedures and the rates of adverse events will also be reviewed by our Community Advisory Board (see Research Plan), our research team and Virtually Better to determine any changes in participant risk. The PI will immediately report any adverse events that are observed to the Lifespan Internal Review Board (IRB) and NIMH. Serious adverse events (SAEs) will be reported to the Lifespan IRB immediately by telephone and by written report within 24 hours of our receipt of information regarding the event; SAEs will also be reported in writing to NIMH. Actions taken by the IRB in response to SAEs will also be reported to NIMH, as will reports of changes or amendments to the protocol as a result of an SAE. Reports of changes or amendments to the protocol in general must be requested first in writing to the Lifespan IRB, which then will grant or deny permission to make the requested change or amendment in protocol. Modifications to study aims or design will also be submitted to NIMH for approval prior to instituting them. Finally, if significant medical or mental health risks occur during the study period evaluation by the Rhode Island Hospital emergency department will be immediately initiated to determine whether hospitalization or urgent care is needed. In the event that a research participant either withdraws from the study or the investigator decides to discontinue a research participant due to SAE, the research participant will be monitored by the investigator via ongoing status assessment until either a resolution is reached (i.e. the problem requiring hospitalization has resolved or stabilized with no further changes expected), the SAE is determined to be clearly unrelated to the study intervention, or the SAE results in death. Outcome of all SAEs will be periodically reported to NIMH. A summary of the SAEs that occurred during the previous year will be included in the annual progress report to NIMH.

Educational Training

Since October 1, 2001, Lifespan has required that researchers and IRB members read Protecting Study Volunteers in Research (Dunn & Chadwick) and complete the related exam. This process has served as an initial certification. In June, 2005, the Office of Research Administration contracted with CITI, a Collaborative Institutional (modular) Training Initiative program, for our Human Subjects Protection and HIPAA training for all research personnel. Currently this program offers researchers a basic human subject's protection course as well as a refresher course that is required every three years. Documentation of successful completion is automatically generated and can be printed directly by the researcher

Additional and continuing education opportunities for clinical researchers include the Office of Research Administration newsletter that is circulated to > 900 recipients every 6 weeks. Relevant information concerning research review is available on the ORA web page at www.lifespan.org/research/. In addition to standard institutional research information, the web page contains links to other sites such as CenterWatch, NIH, PRIM&R/ARENA.
